#### Primary outcome measure

In-hospital post-operative complications of any cause (censored at 30 days following surgery).

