#### Primary objective

To confirm the incidence of 30-day in-hospital complications following elective inpatient surgery.

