#### Study data

Data will be collected on *all eligible patients* who undergo surgery during the study week. The proposed dataset is included in the appendix. Only routine clinical data will be included and where this is unavailable the domain will be left blank e.g. patients who do not require blood tests. It is possible that national groups may supplement their core data set with a very limited number of additional variables if these can be accommodated within the two page case record form (CRF) and they comply with regulations applied to this study.

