#### **Data collection**

Data will be collected in individual hospitals on a paper CRF for each patient recruited. Paper CRFs will be stored within a locked office in each centre. This will include identifiable patient data in order to allow follow-up of clinical outcomes. Data will then be pseudo-anonymised by generating a unique numeric code and transcribed by local investigators onto an internet based electronic CRF. Each patient will only be identified on the electronic CRF by their numeric code. Thus the coordinating study team cannot trace data back to an individual patient without contact with the local team. A patient list will be used in each centre to match identifier codes in the database to individual patients in order to record clinical outcomes and supply any missing data points. Once the local co-ordinator confirms data entry is complete for their hospital they will receive a spreadsheet of raw (un-cleaned) data, allowing further checks for data completeness and accuracy.

ISOS protocol v1.0 Page 7 of 16

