#### 11. MONITORING & AUDITING

ISOS study master documents will be audited by the sponsor to ensure study activities are conducted according to the protocol, the sponsor's standard operating procedures, Good Clinical Practice and the applicable regulatory requirements. In participating hospitals, local study documents may be selected for audit on a local basis. However, the ISOS study team will not routinely monitor data collection in individual hospitals or conduct source data verification.

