## Post-operative Follow Up

Infection							
Wound infection	Mild 🗌	Moderate 🗌	Severe	None 🗌			
Body cavity	Mild 🗌	Moderate 🗌	Severe	None 🗌			
Pneumonia	Mild 🗌	Moderate	Severe	None 🗌			
Urinary tract	Mild 🗌	Moderate 🗌	Severe	None 🗌			
Bloodstream	Mild 🗌	Moderate	Severe	None 🗌			
Cardiovascular							
Myocardial infarction	Mild 🗌	Moderate	Severe	None 🗌			
Arrhythmia	Mild 🗌	Moderate	Severe	None 🗌			
Pulmonary oedema	Mild 🗌	Moderate 🗌	Severe	None 🗌			
Pulmonary embolism	Mild 🗌	Moderate 🗌	Severe	None 🗌			
Cardiac arrest	Mild 🗌	Moderate 🗌	Severe	None 🗌			
Stroke	Mild 🗌	Moderate 🗌	Severe 🗌	None 🗌			
Other							
Gastro-intestinal bleed	Mild 🗌	Moderate 🗌	Severe	None 🗌			
Other post-operative bleed	Mild 🗌	Moderate	Severe	None 🗌			
Acute kidney injury	Mild 🗌	Moderate 🗌	Severe 🗌	None 🗌			
Delirium	Mild 🗌	Moderate 🗌	Severe	None 🗌			
ARDS	Mild 🗌	Moderate 🗌	Severe 🗌	None 🗌			
Anastomotic leak	Mild 🗌	Moderate 🗌	Severe	None 🗌			
Medical error	Mild 🗌	Moderate 🗌	Severe	None 🗌			
Other	Mild 🗌	Moderate 🗌	Severe	None 🗌			
Critical care admission any time during hospital stay? ☐ Y ☐ N							
If yes, day of critical care admission (day 0=day of surgery):							
If yes, duration of critical care stay (days):							
-	, ,	-					
Duration of hospital stay after surgery (days):							
Survival at 30 days after su	☐ Alive	□ Dead					

ISOS protocol v1.0 Page 16 of 16

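### The primary outcome rests on a 19-row form with no shared row criteria, grade anchors or explicit new-or-worsened rule, so incidence and regional rates will partly reflect local diagnostic thresholds

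*Protocol*

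**What the plan says.** The primary objective is an absolute rate: "To confirm the incidence of 30-day in-hospital complications following elective inpatient surgery". Section 7 (Primary outcome measure) defines the outcome as "In-hospital post-operative complications of any cause (censored at 30 days following surgery", and lists no components, criteria or grade threshold.

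The operational content is the appendix page headed "Post-operative Follow Up". It has five infection rows, six cardiovascular rows and eight others. Every row carries the same four boxes, including "Cardiac arrest" and medical error, and the last row is an unspecified Other.

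On data sources, section 6 (Study data) states: "Only routine clinical data will be included and where this is unavailable the domain will be left blank". Under Data collection, entries are "transcribed by local investigators onto an internet based electronic CRF". Section 11 states that "the ISOS study team will not routinely monitor data collection in individual hospitals or conduct source data verification", while "local study documents may be selected for audit on a local basis". Section 6 (Study group organisation) makes the local co-ordinator responsible for staff training and for the quality of the data, without saying what definitions staff are trained to. Section 7 presents the data in 13 named regions and plans single-level and multi-level logistic models.

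**The concern.** An incidence means something only relative to a case definition. Here each hospital decides what counts as pneumonia, delirium or acute kidney injury, and what separates mild from moderate. Because the natural reading of the outcome is a tick in any of 19 rows, small differences in local threshold add up.

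Three gaps matter separately:

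- **Frequency.** Without row criteria, a lenient and a strict hospital with identical patients can report different rates.
- **Severity.** The Introduction says data are needed on how severe complications are as well as how often they occur. Unanchored grades cannot supply that consistently, and it is unclear what a mild cardiac arrest would be.
- **Onset.** A patient with a long-standing arrhythmia, or one whose existing condition worsens, may be ticked in one hospital and not in another. Ticking baseline disease would also create artificial associations with the comorbidities recorded on the same form.

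This cannot be left to an analysis plan. The definitions have to be in the hands of site staff when the form is completed.

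**Working it through.** **No figure to reproduce.** The protocol gives no sample size and no expected complication rate. The arithmetic below is illustrative only, apart from the row count.

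**Row count (appendix, follow-up page).** 5 infection + 6 cardiovascular + 8 other = 19.

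**What the text offers as a common standard.**

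| Element | Supplied text |
|---|---|
| Criterion per row | None, and no definition set cited |
| Meaning of the grades | None |
| Which grades count as an event | Not stated |
| New versus pre-existing | Implied by the word post-operative; no rule for worsening |
| Training | Required locally; content not given |
| Central verification | No routine monitoring or source data verification |
| Local checks | Local guarantor, raw data returned to sites, possible local audit |

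The precedent does not fill the gap. Section 6 (Consent procedures) says the earlier European study used the same methods of data capture, but the Introduction says its dataset did not include complications.

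**Illustration 1: false ticks.** Assumptions: any tick is an event, the false-tick rate f is the same in each row, rows are independent, and true incidence is p.

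- Share of complication-free patients with at least one false tick: 1 − (1 − f)^19.
  - f = 0.1%: 1 − 0.999^19 = 1.9%
  - f = 0.5%: 1 − 0.995^19 = 9.1%
- Apparent incidence: p + (1 − p) × that share. A false tick in a patient who already has a true complication does not change the composite.
  - p = 15%, f = 0.1%: 0.15 + 0.85 × 0.0188 = 16.6%
  - p = 15%, f = 0.5%: 0.15 + 0.85 × 0.0908 = 22.7%
- Gap at p = 15%: 22.7 − 16.6 = 6.1 points. At p = 10% it is 0.90 × (9.08 − 1.88) = 6.5 points, and at p = 20% it is 0.80 × 7.20 = 5.8 points.
- Opposite extreme: if all false ticks fell in the same patients, the affected share would equal f itself, and the gap at p = 15% would be 0.85 × 0.4 = 0.34 points.

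**Illustration 2: missed events.** Assume the same true incidence of 15% in two regions, with 90% of events recorded in one and 70% in the other.

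- Apparent rates: 0.15 × 0.90 = 13.5% and 0.15 × 0.70 = 10.5%.
- Odds ratio: (0.135/0.865) / (0.105/0.895) = 1.33, with no true difference.

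Shared definitions would reduce the first problem. They would reduce the second only in part, because hospitals would still differ in what they test for.

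**The case against.** The other side has several good points.

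- **Checking exists.** A reader might infer that the outcome is never verified. The documents do not support that. Section 11 rules out routine monitoring and source data verification by the study team but allows local audit, and section 6 provides a local guarantor and returns raw data to sites for accuracy checks. What stands is that these checks are local and have no common definition to check against.
- **Some repair is possible.** A reader might infer that nothing can be done after data collection. In fact each row carries a grade, so analysts could restrict to moderate or severe events, drop the open rows or analyse single complications. Sites also hold a patient list and can be queried. These repairs are partial because the grades themselves are unanchored.
- **Onset is implied.** A reader might infer that baseline conditions are freely countable. The outcome and the form heading both say post-operative, and the pre-operative page records some comorbidities separately. The gap is the lack of an explicit rule, above all for worsening of an existing condition.
- **Models and reporting soften the regional point.** The plan presents regions and bars comparison of individual nations. Hospital-level terms in the multi-level models may absorb some threshold differences in the risk-factor analyses. They do not correct the crude incidence or the rates shown by region.
- **The appendix text is incomplete as supplied.** A separate definition sheet may exist. The text shown refers to none.

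**Conclusion.** The point stands as a weakness in the stated instrument. On the supplied text, the primary incidence and the regional rates will partly reflect local diagnostic thresholds, and later analysis can only partly correct this.

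The size cannot be derived from the protocol. The gap of about 6 points depends on assumed false-tick rates of 0.1% and 0.5% per row, independent rows and a true incidence of 15%; clustering could bring it well below that. A reader might subtract 1.9% from 9.1% and quote about 7 points on the primary incidence. Those percentages apply only to complication-free patients, so the full difference would hold only if true incidence were near zero. Nor do the documents support saying that any regional difference actually observed would be artefact, only that part of it could not be told apart from one.

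**What to change.** Before the first cohort week, attach a short definition sheet to the case record form and cite it in section 7 (Primary outcome measure). If a sheet already exists, cite it there. It should:

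- give a minimum criterion for each named complication, based on what routine notes contain;
- state that only conditions new or worsened after the index operation are ticked;
- anchor mild, moderate and severe by consequence, using one stated scale, and say which grades count towards the primary outcome and which do not apply to a given row.

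Report the open rows, Other and Medical error, separately, because a minimum criterion is hard to write for them. Add a sensitivity analysis of the primary incidence without them.

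The cost is slightly longer site training and some extra translation, with no new data items or tests. Some ticks that would have counted no longer will. Differences in what hospitals test for will remain under routine-data collection, and the report should say so when it interprets the regional rates.

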#### Secondary outcome measures

- In-hospital all-cause mortality (censored at 30 days following surgery)
- Admission to critical care (within 30 days following surgery)
- Duration of hospital stay (duration of primary hospital stay after surgery)

ISOS protocol v1.0 Page 9 of 16

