#### Secondary objectives

- 1. To confirm the 30-day in-hospital mortality associated with these complications
- 2. To describe the relationship between critical care admission and postoperative complications
- 3. To describe the effect of post-operative complications on duration of hospital stay

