#### 6. STUDY PROCEDURES

#### **Consent procedures**

The requirement for patient consent will vary according to regulations in the participating nations. During the European Surgical Outcomes Study (EuSOS), which used identical methods of data capture, investigators were required to take written informed consent in only one of 28 nations. We anticipate that patient consent will not be required most nations taking part in ISOS on the basis that the dataset will only include variables documented as part of routine clinical care (see appendix) and that

ISOS protocol v1.0 Page 6 of 16

identifiable patient data will not leave the hospital where each individual patient is treated. Unless written informed patient consent is provided, only anonymised or coded data will be provided to the ISOS study group.

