#### **End of Study Definition**

The end of the study is defined as the end of the 30-day follow-up for the last patient included. Data analysis shall follow this.

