#### Statistical analysis

Hospitals including data describing less than 20 valid patients will be excluded in the data analysis. Data will be presented in the following geographical regions: Australasia, North America, Central & South America, Western Europe, Eastern Europe, Northern Europe, Southern Europe, Indian sub-continent, Middle East, China & South-East Asia, North Africa, Sub-Saharan Africa and Central Asia. No comparison will be made between individual nations and all national and institutional level data will be anonymised prior to publication. Categorical variables will be described as proportions and will be compared using chi-square or Fisher's exact test. Continuous variables will be described as mean and standard deviation, if normally distributed, or median and inter-quartile range, if not normally distributed. Comparisons of continuous variables will be performed using one-way ANOVA or Mann-Whitney test as appropriate. Univariate analysis will be performed to test factors associated with post-operative complications, admission to critical care and in-hospital death. Single-level and hierarchical multi-level logistic regression models will be constructed to identify factors independently associated with these outcomes and to adjust for differences in confounding factors. Factors will be entered into the models based on their univariate relation to outcome (p<0.05), biological plausibility and low rate of missing data. A stepwise approach will be used to enter new terms. Results of logistic regression will be reported as adjusted odds ratios (OR) with 95% confidence intervals. The models will be assessed through the use of sensitivity analyses to explore possible interacting factors and examine any effect on the results. A single final analysis is planned at the end of the study.

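### The mortality outcome is death in hospital, but the visible CRF records only vital status at 30 days, so a death with a stay under 30 days cannot be classified

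*Protocol*

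**What the plan says.** Three places in the protocol make death in hospital the mortality endpoint.

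- Secondary objectives, item 1: "To confirm the 30-day in-hospital mortality associated with these complications".
- Section 7, Secondary outcome measures: "In-hospital all-cause mortality (censored at 30 days following surgery".
- Section 7, Statistical analysis: "Univariate analysis will be performed to test factors associated with post-operative complications, admission to critical care and in-hospital death". Single-level and multi-level logistic models for the same three outcomes follow.

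The appendix CRF (Post-operative Follow Up page) has two fields that bear on this endpoint:

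- "Survival at 30 days after su", with boxes for Alive and Dead. The label breaks off mid-word in the extracted text.
- "Duration of hospital stay after surgery (days", which does not show whether the stay ended in death or live discharge.

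Three other statements set the context. Under End of Study Definition, "The end of the study is defined as the end of the 30-day follow-up for the last patient included". Under Consent procedures, "the dataset will only include variables documented as part of routine clinical care". Under section 11, "the ISOS study team will not routinely monitor data collection in individual hospitals or conduct source data verification".

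**The concern.** The endpoint and the field that feeds it describe different events. Death in hospital by day 30 is a subset of death anywhere by day 30, and the visible form records only the latter. An analysis plan cannot repair this, because it cannot recover a distinction that the data do not carry.

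The protocol also does not say what a site should do about a patient who goes home before day 30. One site might trace the patient and enter true 30-day status. Another might enter Alive because the patient left alive. A third might leave the item blank, as section 6 (Study data) allows for unavailable data. With no routine source data verification, nothing central would reconcile these readings.

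Three uses of the data are exposed:

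- The mortality figure itself.
- The link between complications and death in secondary objective 1. The primary outcome counts only in-hospital complications, so a death after discharge can appear as a death with no recorded complication.
- The regional presentation and the multi-level model for in-hospital death, where differences in access to post-discharge information could look like differences in mortality.

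**Working it through.** The protocol gives no figure to reproduce on this point. The check has two parts.

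**1. Can the outcome be derived from the two fields?**

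Every combination of death day (0 to 30, or no death by day 30) and live-discharge day (0 to 40) was mapped to the pair (30-day status, length of stay). A death on or before the discharge day counts as in hospital, and the stay then ends on the day of death. An outcome is derivable if each recorded pair corresponds to one in-hospital-death status only.

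| 30-day status | Length of stay | In-hospital death by day 30? |
|---|---|---|
| Alive | any | No, always |
| Dead | 30 days or more | Yes, always |
| Dead | 0 to 29 days | Undetermined at each of the 30 values |

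For example, Dead with a stay of 5 days fits a death in hospital on day 5. It fits equally well a discharge on day 5 and a death at home on day 20. A patient who is dead by day 30 cannot have stayed beyond day 30, so in consistent records the settled Dead row is a stay of exactly 30 days. Nearly every possible Dead record is therefore ambiguous.

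The ambiguity runs one way. If Dead is taken as death in hospital, the count can only be too high. A site that enters Alive for a patient who left alive still gives the right in-hospital answer.

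Admission to critical care is handled differently. It has its own day-of-admission field, so its 30-day window can be derived. Death has no equivalent visible field.

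**2. How large could the effect be?**

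Inputs:

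- In-hospital mortality p. The introduction cites reported hospital mortality of 1 to 4%; both ends are used as illustrations.
- Share f of 30-day deaths that occur after discharge. This is not in the documents; 10%, 20% and 30% are assumed.

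In-hospital deaths are a fraction (1 - f) of all 30-day deaths, so all-place 30-day mortality = p / (1 - f).

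| f | Ratio 1/(1 - f) | p = 1% reads | Extra deaths per 10,000 patients | p = 4% reads | Extra deaths per 10,000 patients |
|---|---|---|---|---|---|
| 10% | 1.11 | 1.11% | 11 | 4.44% | 44 |
| 20% | 1.25 | 1.25% | 25 | 5.00% | 100 |
| 30% | 1.43 | 1.43% | 43 | 5.71% | 171 |

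These ratios compare a site that finds every post-discharge death with one that finds none. If a site finds only a share t of them, the ratio is 1 + t × f/(1 - f). With t = 50% and f = 20% it is 1 + 0.5 × 0.25 = 1.125, half the excess of full tracing.

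**The case against.** The strongest objection concerns the evidence. The CRF label stops mid-word, and this part of the form was not read cleanly. A qualifier such as censoring at discharge, or a further field, could be present on the source page, and a clear discharge qualifier would remove the mismatch. This stands as a condition on the point. The visible text names a 30-day time point and carries no in-hospital qualifier.

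The protocol also uses in-hospital death consistently, provides for staff training before data collection, calls the appendix a proposed dataset, and gives each site a patient list for follow-up. Completion guidance may exist elsewhere. That makes divergent recording less likely, but a form that names a different time point and omits discharge status still invites it.

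Four stronger readings are tempting, and the documents do not support them:

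- *The outcome cannot be derived at all.* Every Alive record settles it, and so does Dead with a stay of 30 days or more. The unresolved records are deaths, which are few if mortality lies in the 1 to 4% range cited in the introduction.
- *Sites will record different things.* No statement shows this. It is a possibility that follows from the missing instruction and the lack of verification.
- *The protocol treats 30-day survival after discharge as needing consent or registry linkage.* Section 6 says only that consent may open the way to linkage, and section 8 (Ethics) speaks of medium-term outcomes such as one year.
- *The inflation factors estimate the actual error.* They depend on an assumed f and an extreme contrast between sites.

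Mortality is a secondary outcome, the primary outcome is unaffected, and section 7 rules out comparison of individual nations. These points limit the seriousness. Regional presentation and the in-hospital death model remain exposed.

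**Conclusion.** The point holds in a limited form. As the CRF can be read, death in hospital by day 30 cannot be told from death after live discharge when the record shows Dead and a stay of 0 to 29 days. All other patterns with a recorded status are resolved. Whether sites would in practice differ is an inference, and the size of any distortion cannot be found from the documents. Under an assumed post-discharge share of 10 to 30% of 30-day deaths, full tracing would raise the figure to between 1.11 and 1.43 times the in-hospital value; partial tracing would raise it less.

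The conclusion rests on the truncated label having no discharge qualifier and on no unread field giving discharge status or the place or date of death. On that footing this should be fixed. It does not threaten the primary outcome. Once the data are in, the only remedy would be to go back to each hospital.

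**What to change.** First check the source page of the CRF. If the label already restricts the item clearly to the hospital stay, no change is needed.

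Otherwise, before the study week, change the item to status at the end of the primary hospital stay, or at day 30 if still an in-patient. Offer three options: discharged alive, still in hospital, died in hospital. Record the post-operative day with it. Use this item alone for the in-hospital death outcome and its models.

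If 30-day survival is also wanted, keep it as a separate item with an option for status unknown after discharge, and do not use it for the in-hospital outcome.

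The cost is one reworded or additional line on the two-page form and its electronic copy. The in-hospital item uses information that the hospital already holds and needs no further follow-up.

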### 2. SUMMARY/SYNOPSIS

Short title	ISOS study				
Methods	International, 7-day observational cohort study of complications following elective surgery				
Research sites	Hospitals undertaking elective surgery worldwide				
Objective	To provide detailed data describing post-operative complications and associated mortality				
Number of patients	Not specified. All eligible patients undergoing surgery during the study week.				
Inclusion Criteria	All adult patients (aged ≥18 years) undergoing elective surgery during the 7 day study period with a planned overnight stay				
Statistical analysis	Univariate analysis will be used to test factors associated with surgical complications, admission to critical care and in-hospital death. Single and multi-level logistic regression models will be constructed to identify factors independently associated with these outcomes and to adjust for differences in confounding factors. A stepwise approach will be used to enter new terms. A single final analysis is planned at the end of the study.				
Proposed Start Date	A seven day period between April and June 2014				
Proposed End Date	Data collection will end by August 2014				
Study Duration	Four months				

ISOS protocol v1.0 Page 4 of 16

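### Objective 3 asks for the effect of complications on hospital stay, but the only stated comparison of stay is unadjusted, and stay alone has no day-30 limit or stated handling of deaths

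*Protocol*

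**What the plan says.** The third item under Secondary objectives is "To describe the effect of post-operative complications on duration of hospital stay".

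Under Secondary outcome measures, the matching outcome is "Duration of hospital stay (duration of primary hospital stay after surgery"). Its two neighbours carry a time limit: "In-hospital all-cause mortality (censored at 30 days following surgery") and "Admission to critical care (within 30 days following surgery"). So does the primary outcome: "In-hospital post-operative complications of any cause (censored at 30 days following surgery").

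The End of Study Definition reads: "The end of the study is defined as the end of the 30-day follow-up for the last patient included". The Synopsis adds a calendar limit: "Data collection will end by August 2014".

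The Statistical analysis section names three outcomes for univariate testing and for single-level and multi-level logistic models: complications, critical care admission and in-hospital death. The stated purpose of the models includes adjustment for confounding. Stay is not among the three. The sentence that does reach it is: "Comparisons of continuous variables will be performed using one-way ANOVA or Mann-Whitney test as appropriate".

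The case record form asks for days in hospital after surgery and, separately, for survival at 30 days. As far as the extracted form shows, there is no entry for a patient still in hospital at day 30. Complications are graded by severity but not dated, whereas critical care admission is given a day.

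**The concern.** The protocol recognises confounding for three outcomes and plans to adjust for it. It then leaves the one relationship that it words as an effect to a two-group or several-group test without covariates. Patients who develop complications tend to be sicker and to have had larger operations, and both lengthen stay by themselves.

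Three further features bear on the same contrast:

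- The exposure is a complication recorded in hospital, so a patient who stays longer has more time to acquire one. A difference in stay would appear even if complications had no effect on discharge.
- A stay that ends in death is short for a reason unrelated to recovery, and deaths fall mainly among patients with complications.
- A patient still in hospital on day 30 has no defined value. A site could leave the field blank, enter 30, or wait and enter a later figure.

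At stake is how one of three secondary objectives can be interpreted. The primary outcome is not affected.

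**Working it through.** The protocol states no figure for stay, so there is nothing to reproduce. The check has a textual part and an illustrative part.

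**1. Time windows.** Complications: 30 days. Mortality: 30 days. Critical care admission: 30 days. Stay: none. Follow-up: 30 days. Surgery weeks run from April to June 2014 and data collection ends by August, so an April patient could be followed well past day 30 and a late-June patient hardly at all. Whether a longer stay is captured therefore depends on site and date.

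**2. Methods.** Adjusted models cover complications, critical care admission and death. For stay, the stated methods are ANOVA or Mann-Whitney, which use no covariates and do not allow for hospital clustering.

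**3. Time-dependent bias, with no true effect of complications.** Assumed, not from the protocol: exponential stay with mean 4 days (discharge rate λ = 0.25 per day) and a constant complication hazard c = 0.05 per day.

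- Share with a complication: c/(λ + c) = 0.05/0.30 = 16.7%.
- Mean stay without a complication: 1/(λ + c) = 1/0.30 = 3.33 days.
- Mean stay with one: 1/(λ + c) + 1/λ = 3.33 + 4.00 = 7.33 days.
- Spurious difference: 4.00 days.

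This depends on when complications arise. I held the share at 16.7%, confined the hazard to the first days, and repeated the exercise with a log-normal stay (median 3.5 days, log-SD 0.8):

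| Hazard acts during | Mean gap, exponential | Mean gap, log-normal |
|---|---|---|
| first day | 0.55 days | under 0.1 days |
| first 2 days | 1.1 days | 0.4 days |
| first 5 days | 2.3 days | 1.5 days |
| whole stay | 4.0 days | 3.9 days |

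The sign is the same throughout; the size runs from near zero to about 4 days.

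**4. Deaths.** The Introduction gives hospital mortality of 1 to 4%. Assumed: 10% or 20% with complications; log-normal stay with median 4 days without and 10 with (log-SD 0.7 and 0.8); 80% of deaths among patients with complications; death at a uniform point of the stay that would have occurred. With no stay cut by death, the median difference is about 6.0 days. With stays ending in death entered as observed:

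| Mortality | Complications | Median difference | Mean difference |
|---|---|---|---|
| 1% | 20% | 5.7 days | 8.3 days |
| 1% | 10% | 5.5 days | 8.1 days |
| 4% | 20% | 5.1 days | 7.6 days |
| 4% | 10% | 4.1 days | 6.5 days |

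The mean difference without deaths is 8.6 to 8.7 days.

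**5. Stays over 30 days.** In the scenarios of step 4, capping at 30 lowers the mean difference by a further 1.0 to 1.3 days (for example 8.34 − 7.07 = 1.27) and leaves the medians unchanged.

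**6. Confounding.** Adding an assumed severity score (log-odds 0.7 for a complication, 0.3 on log stay) at 20% complications, the ratio of geometric-mean stay is 2.91 unadjusted and 2.40 adjusted at about 1% mortality: 2.91/2.40 = 1.21. At about 4% it is 2.61 and 2.15: 2.61/2.15 = 1.21. Omitting adjustment inflates the ratio by about 21% in this scenario.

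**The case against.** The objective is worded as a description, in a study whose Ethics section likens it to a large clinical audit. An unadjusted comparison of medians is a legitimate description, and nothing in the protocol promises a causal reading. That stands: the contrast is not invalid, and the problem is confined to reading it as an effect.

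A reader might infer that the plan counts deaths as short stays. It contains no such rule. It is silent, the form records 30-day survival separately, and the handling of deaths may be set out in an analysis plan that is not at hand. The silence matters only because the stated method, applied to the field as it stands, would not separate the two kinds of short stay.

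A reader might also infer that long stays are certain to be truncated. Data collection to August allows many to be recorded in full, and a rank test or median is barely moved by a cap. What remains is an undefined cut-off, open to inconsistent entry.

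Finally, the 4-day figure needs a complication hazard that stays constant for the whole stay. The documents do not support that over an early hazard, which gives far less. Dating the first complication at every site, on a form limited to two pages, is a real burden and a debatable trade-off.

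None of this answers the central mismatch: three outcomes are adjusted for confounding, and the one tied to an effect is not.

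**Conclusion.** The point holds as a moderate one for a single secondary objective. From the protocol's own text, the only stated comparison of stay is unadjusted, stay is the only listed outcome without a day-30 limit, and no treatment of stays ending in death is given.

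It would go too far to conclude that the result will be wrong or that its net direction is known. Confounding and time-dependent bias push the difference up; deaths pull it down. All sizes rest on assumed stay distributions, complication rates and hazards. Within those assumptions, the time-dependent part is near zero to about 4 days, deaths lower the median difference from about 6.0 to between 4.1 and 5.7 days, and missing adjustment inflates the ratio of stay by about 21%. These components come from different illustrative scenarios and should not be added together. The supportable conclusion is that the planned contrast describes an association and cannot carry the word effect.

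**What to change.** - Define the outcome as days from surgery to live discharge from the primary hospital stay, censored at day 30, and add a form entry for patients still in hospital at day 30. Make sure the form shows whether a stay ended in death; its survival item is cut short in the text at hand.
- Add a model of time to live discharge with in-hospital death as a competing event. Adjust for the baseline and surgical covariates already on the form, such as age, comorbidity, procedure category and severity of surgery, and allow for clustering by hospital.
- Keep median and inter-quartile range of stay by complication status as a descriptive table.
- Reword objective 3 as an association, and state the time-dependent bias as a limitation, since adjustment for baseline covariates does not remove it.
- Optional: record the day of the first complication and enter complications as a time-varying exposure. This addresses the time-dependent bias directly but adds work at every site.

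Without the optional item, the cost is one extra regression, a few words in the protocol and a small change to the form. No extra follow-up is needed.
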